### ***3.1.1.1. Dose Escalation and Stopping Rules***

As detailed in [Section 4.4](#), a DMC will be formed to independently review the safety data from previous dose level(s) and make recommendations on whether dose escalation should continue. Based on the DMC recommendation, following review by the sponsor, the doses may be escalated or reduced and may be lower than the starting dose.

The starting treatment dose of lutetium-177 in Part 1 will be 10 mCi. Planned dose escalations (with a 3+3 design) are 25, 50, 65, and 85 mCi. Up to 1 additional dose level may be recruited to investigate an intermediate dose of investigational medicinal product (IMP), if warranted based on the safety findings from previous dose level(s). The requirement for an additional dose level will be agreed with the sponsor in consultation with the DMC and will be documented in the

Trial Master File. Dosing at any additional dose level will be subject to the same dose-escalation rules as for the planned dose levels, as described below. The maximum planned dose is 85 mCi.

Initially, 1 patient will be allocated to Dose Level 1 and subsequent dose escalations will be conducted using a classic 3+3 design. If no treatment-related Grade 3 or higher AEs are observed in the first patient, escalation from Dose Level 1 to Dose Level 2 will proceed with 3 patients being allocated to Dose Level 2, after DMC evaluation and recommendation. If a Grade 3 or higher treatment-related AE occurs, a further 2 patients will be enrolled at Dose Level 1.

The DMC will receive all SAE on an ongoing basis. The DMC will make the final assessment of whether the event qualifies as a DLT.

The first enrolled patient in each dose level will be observed for a minimum of two weeks after the treatment dose before subsequent patients will be dosed at the same dose. During the two weeks of observation, safety surveillance will focus on DLTs (including myelosuppression). If a DLT is observed in the first patient, a second patient will be included and observed for a minimum of two weeks after the treatment dose before the third patient is included. If no DLT is observed in the first patient, two subsequent patients will receive the treatment dose, but at least two days apart.

Escalation and de-escalation decisions will then be determined by the number of DLTs (as defined in [Section 3.1.1.2](#)) observed during Cycle 1 and the number of patients evaluable for DLTs, as follows.

- If no DLT is observed in the initial 3-patients at each dose level, 3 patients will be enrolled into and dosed in the next dose level. Dose escalation will continue in this manner until a DLT is observed or the highest planned dose level has been completed.
- If 1 DLT is observed in the initial 3-patients at each dose level, an additional 3 patients will (if recommended by the DMC) be enrolled at that dose level.
  - If no further DLTs are observed among the 3 additional patients (i.e., the total number of DLTs in the 6-patient dose level is 1), dose escalation will proceed with 3 patients being enrolled into the next dose level.
  - If  $\geq 1$  DLT is observed among the 3 additional patients (i.e., the total number of DLTs in the 6-patient dose level is  $\geq 2$ ), dose escalation will be stopped by the sponsor, upon consultation with the DMC.
    - If warranted, dosing may proceed with 3 patients being enrolled into an additional dose level that is intermediate between that of the current and the previous dose level. If dose escalation is stopped, the dose level immediately below that at which the DLTs were observed will be considered the MTD.
- If 2 or 3 DLTs are observed in the initial 3-patients at each dose level, dose escalation will stop. If warranted, dosing may proceed with 3 patients being enrolled into an

additional dose level that is intermediate between that of the current and the previous dose level. Otherwise, the dose level immediately below that at which the DLTs were observed will be considered the MTD. No further patients will be enrolled into the current dose level.

If only 3 patients were treated at the dose level below the intolerable dose 3 more patients will be recruited at that dose level to ensure that no more than 1 DLT occurs out of 6 patients.

Doses will be escalated until:

- The highest planned dose level has been found to be tolerated (i.e., stopping criteria were not met), or
- A toxic dose level has been identified.

When the dose-escalation phase of the trial has stopped due to toxicity, the MTD is identified as the highest non-toxic dose level (see [Section 3.1.2](#)).

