### 3.1.1. Part 1 (Dose-escalation Phase)

Part 1 will comprise 1 dose level consisting of a single patient followed by additional dose levels that use a 3+3 design (see [Figure 1](#)).

In the first 5-week treatment cycle, a 5 mCi dosimetry dose will be administered on Day 1 and a treatment dose (according to the assigned dose level, as listed below) will be administered on Day 8 (see [Figure 1](#) for a schematic of a treatment cycle in Part 1). However, if a patient experiences a Grade 3 or 4 non-hematologic AE (including an AE considered to be a Grade 3 or 4 nervous system disorder) or other DLT after receiving the dosimetry infusion, the treatment dose will not be administered, and the patient will be discontinued from trial treatment. If the dosimetry dose of 5 mCi turns out to deliver a too low acquisition of radioactivity count (see [Section 7.2](#)), the dosimetry dose will be increased to 10 mCi for subsequent patients, at the sponsor's discretion.

A fixed mass dose of approximately 1 mg DTPA-omburtamab will be labelled with increasing radioactivity doses. This mass dose was selected based on the clinical experience with iodine-labelled omburtamab, in which the same mass dose has been shown to be stable and to support clinical use in concentrations up to 100 mCi/ml. The planned radioactivity dose levels are:

- Dose Level 1 (1+2 patients): 10 mCi
- Dose Level 2 (3+3 design): 25 mCi
- Dose Level 3 (3+3 design): 50 mCi
- Dose Level 4 (3+3 design): 65 mCi
- Dose Level 5 (3+3 design): 85 mCi.

A maximum of 1 additional intermediate dose level may be added to the trial if warranted based on the findings from previous dose levels (see [Section 3.1.1.1](#)).

[figure not shown]
Patients who are not discontinued from treatment (according to the criteria in [Section 4.3.2](#)) will be eligible for a second treatment cycle at the same dose administered in the first cycle. The second treatment cycle will not include a dosimetry dose but will instead consist of a treatment dose on Day 1 of the cycle.

In Part 1, the patients will receive a maximum of 2 treatment cycles. Patients who do not experience a DLT will be eligible for Cycle 2 dosing at the same dose administered in Cycle 1. Cycle 2 dosing will not include a dosimetry dose but only a treatment dose on the first day of the cycle.

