### ***3.1.1.2. Definition of Dose-limiting Toxicity***

DLTs are defined as AEs (graded according to CTCAE version 5) occurring within 5 weeks after first IMP administration in Cycle 1 of Part 1 and that are considered possibly or probably related to IMP and meet any of the following criteria:

- Grade 4 myelosuppression (i.e., anemia, thrombocytopenia, or neutropenia) lasting more than 1 week, or more than 3 weeks following intervention (e.g., blood transfusion or granulocyte-macrophage colony-stimulating factor [GM-CSF])
- Any other Grade 4 hematological AE
- Grade  $\geq 3$  thrombocytopenia associated with bleeding
- Grade  $\geq 3$  febrile neutropenia (i.e., fever concurrent with neutropenia) lasting more than 5 days despite use of growth factors and antibiotics
- Grade 4 infusion-related reactions/anaphylaxis
- Grade 3 infusion-related reactions (excluding fever and Grade 3 abnormal laboratory values) that do not resolve to Grade  $\leq 1$  within 5 days of onset.
- Any non-hematological Grade  $\geq 3$  AE that is not listed in the list of exemptions below

DLTs must be entered onto the clinical AE report form and be reported from site to sponsor within 24 hours of the investigator's first knowledge of the event (see [Section 7.4.5.2](#)). If any of the side effects mentioned in the DLT definitions occur during Cycle 2 in Part 1, these will be discussed at the first upcoming preplanned DMC meeting, and the Sponsor Safety Committee will evaluate the DMC recommendations for further dosing.

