#### **4.4. *Data Monitoring Committee***

An external DMC will be established to assure patient safety and will function independently of all other individuals associated with the conduct of the trial, including site investigators participating in the trial. The DMC will consist of a minimum of 2 physicians whose expertise covers relevant specialties.

During the conduct of Part 1, following completion of the first 5-week treatment cycle (Cycle 1) for the last patient in each dose level, the DMC will evaluate available safety information and recommend trial continuation or termination. If continuation is recommended, the DMC will recommend to the sponsor whether the dose should be escalated, de-escalated, or held at the same level. In the absence of DLT during the first two weeks of the first patient enrolled in each dose level, the enrollment to the dose level will continue without the need of feedback from the DMC.

If any of the side effects mentioned in the DLT definitions ([Section 3.1.1.2](#)) occurs during Cycle 2 in Part 1, these will be discussed at the first upcoming preplanned DMC meeting, and the internal Sponsor Safety Committee will evaluate the external DMC recommendations for further dosing. During Part 1 and until the DMC meeting in Part 2, the sponsor will share with the DMC all SAEs occurring during the trial and an unplanned DMC meeting can be held at the request of either the DMC or the Sponsor Safety Committee.

The DMC will evaluate the totality of cumulated absorbed dose calculated based on the dosimetry data from Part 1, and all available DLTs and other non-DLT toxicities from cycles 1 and 2 in all patients dosed in Part 1, to guide whether the maximum of five cycles is feasible in Part 2.

During the conduct of Part 2, an additional DMC meeting will be held when the eighth patient has completed dosing in Cycle 1 to evaluate whether the trial should be modified, stopped, or continue unchanged. The Sponsor Safety Committee will evaluate the recommendations from the DMC after each DMC meeting. Any significant finding/recommendation from the DMC and endorsed by the Sponsor Safety Committee will be communicated to the regulatory authorities and Institutional Review Board (IRB)/Ethics Committee (EC) as appropriate, and to the sites.

Responsibilities, procedures, content of the DMC packages, and workflow of the DMC are specified in the DMC Charter.

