## **8.5. Safety Analysis**

### **8.5.1. Dose-Limiting Toxicities**

DLTs observed during the DLT evaluation period, i.e., within 5 weeks after the dosimetry dose in Cycle 1 of the dose escalation will be listed and summarized by Medical Dictionary for Regulatory Activities (MedDRA) system organ class (SOC) and preferred term (PT). DLTs observed outside the DLT evaluation period will be presented in a listing. The information from

the DLTs will be used to guide the escalation and ultimately determine the MTD. Furthermore, the information will be used to make recommendations regarding the RP2D. The evaluation of DLTs will be based on the DLT evaluable analysis set.

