 The Lu-DTPA-omburtamab Treatment Period is divided into 5-week cycles. In Part 1, the patient can receive up to 2 cycles at the discretion of the investigator. Cycle 1 starts with a dosimetry dose on Day 1 and continues with the first treatment dose on Day 8 (adjustments to the dosing schedule will be accommodated on a patient-by-patient basis depending on the clinical condition of the patient). The infusion reservoir must be flushed with HSA and CSF after each infusion. On dosing days, all assessments are done before dosing.

 If the IMP is discontinued after Cycle 1, the Day 29 Visit is replaced by the EOT Visit.

 Informed consent must be obtained before any trial-related procedures. If the indwelling ICV access device (e.g., Ommaya) is placed in connection with the tumor resection, the informed consent must be obtained prior to the surgery, and before the start of the screening period, unless this is placed as part of a standard of care procedure at site. If any procedures/tests are from before informed consent is obtained, it must be clear from source documents that this was not performed for the purpose of the present trial. In these cases, the procedures/tests do not need to be repeated at the Screening Visit if they were performed within the allowed timelines. The investigator is responsible for documenting this properly.

 Physical examinations to be performed at screening and as clinically indicated.

 Measurements of heart rate, respiratory rate, temperature, and blood pressure. On dosing days, measurements to be taken before and 30 min after the end of the IMP infusion.

 Lansky Scale <16 years, Karnofsky Scale ≥16 years.

 To be performed within 3 weeks prior to the first IMP infusion. May be performed on the first dosing day but it must be before IMP administration.

 MRI of the brain and spine will be completed before first IMP administration, at the EOT Visit (preferably ±4 days of the actual visit date). MRI can be performed on a separate day to the other visit assessments, if required, in accordance with investigational site standards.

 Will be used to evaluate safety and efficacy.

 Beginning 24 hours before IMP administration, divided into twice-daily doses for a total of 3 days.

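### At Dose Levels 2–5, the two-week sentinel rule can clear two more children for treatment while the first has a Grade 4 anemia, neutropenia or non-bleeding thrombocytopenia too recent to count as a DLT

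*Combined protocol and SAP*

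**What the plan says.** **Timing.** In Part 1 Cycle 1, the dosimetry dose is given on Day 1 and, under Section 3.1.1, "a treatment dose (according to the assigned dose level, as listed below) will be administered on Day 8".

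**Sentinel step.** Section 3.1.1.1 requires at least two weeks of observation of the first patient after treatment "before subsequent patients will be dosed at the same dose". It names myelosuppression among the things to look for in that time. If there is no DLT: "If no DLT is observed in the first patient, two subsequent patients will receive the treatment dose, but at least two days apart". If there is a DLT, a second patient is taken and observed for at least two weeks after treatment before the third. Section 4.4 adds that, with no DLT in the first patient's first two weeks, "the enrollment to the dose level will continue without the need of feedback from the DMC".

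**DLT definition.** Section 3.1.1.2 lists "Grade 4 myelosuppression (i.e., anemia, thrombocytopenia, or neutropenia) lasting more than 1 week, or more than 3 weeks following intervention". It also lists hematological events that do not face this test: every other Grade 4 hematological event, and Grade 3 or higher thrombocytopenia with bleeding. Febrile neutropenia has its own 5-day test.

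**Counts.** Table 6 (Appendix 3) schedules hematology on Days 15, 22 and 29 after the Day 8 treatment, each ±1 day.

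**Dose Level 1** works differently. It has a single patient, and any treatment-related event of Grade 3 or higher triggers enrolment of two more at that level.

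**The concern.** The sentinel period is meant to catch myelosuppression, but its trigger is a DLT, and the relevant DLT has a duration test half as long as the period itself. An event that starts in the second of the two weeks cannot have met the test when the period ends. The written rule then treats the first child as clear.

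Myelosuppression is foreseeable here. Section 1.2.1 reports cytopenia-related events in 81.7% and 87.5% of patients in the two trials of the iodine-labelled antibody, and Section 3.3.3 gives myelosuppression in mice as the reason for the 10 mCi start. The single patient at 10 mCi is covered by a Grade 3 trigger. At 25 to 85 mCi, an ongoing Grade 4 count may trigger nothing.

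At stake is a stagger and a look. The second and third children may be treated two days apart with no DMC feedback. Had the event already been classed as a DLT, the third child would have waited at least two weeks after the second was treated.

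**Working it through.** The plan gives no figure to reproduce here. The check is a day count.

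**Inputs.** Treatment on Day 8 (3.1.1); sentinel minimum 14 days and two-day spacing (3.1.1.1); duration of more than 7 days, or more than 21 days following intervention (3.1.1.2); counts on Days 15, 22 and 29, ±1 day (Table 6); DLT window of 5 weeks from the first dose (3.1.1.2).

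**1. When the period ends.** Day 8 + 14 = Day 22, which is post-treatment day 14.

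**2. Which onsets are still undecided.** An onset on post-treatment day s has lasted 14 − s days. It can be a DLT only if 14 − s > 7, that is, s < 7.
- s = 6: 8 days, can be a DLT.
- s = 7: 7 days, not more than a week.
- s = 8 to 14: 6 down to 0 days, cannot be.

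Counting onset days 0–13, 7 of 14 are undecided (50%). Counting days 1–14, it is 8 of 14 (57%).

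**3. The intervention limb.** 14 − s > 21 has no solution for s ≥ 0. Where this limb applies, no post-treatment onset can qualify before post-treatment day 22. Section 6.2 restricts hematological support in Cycle 1, but Section 6.3 allows it for myelosuppression.

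**4. What scheduled counts can show.** 22 − 15 = 7 days, not more than 7. Over the ±1-day windows (Days 14, 15, 16 against 21, 22, 23) the interval runs from 5 to 9 days. It exceeds 7 in 3 of 9 combinations: 14–22, 14–23 and 15–23.

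**5. If the next patients' dosimetry also waits for clearance.** Their treatment falls on the sentinel's Day 22 + 7 = Day 29, post-treatment day 21. An onset is then decided if 21 − s > 7, that is, s < 14. The undecided share is 0 of 14 or 1 of 14 (0–7%). This needs a re-check. A count is scheduled on Day 29, but no text ties the next treatment doses to its result. A Grade 4 value first seen on Day 22 and still present on Day 29 again spans only 7 days.

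**6. Stagger lost.** At least 14 days becomes at least 2: 14 − 2 = 12 days.

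**7. Time needed to settle every such onset.** Under the 1-week limb, an onset on post-treatment day 14 first exceeds 7 days on day 14 + 8 = 22. That is inside the post-treatment part of the DLT window, 35 − 7 = 28 days.

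**The case against.** **The larger share may rest on the less natural reading.** Section 4.4 says that it is enrolment that continues after two weeks, Section 3.1.1.1 speaks of later patients being included, and Section 8.2 counts the dosimetry dose as trial treatment. On that reading step 5 applies. The no-DLT condition in 3.1.1.1 also has no cut-off at Day 22: an event that passes one week before the next treatment doses would be an observed DLT. Much of this stands. But 3.1.1.1 restricts only dosing at the same dose, so earlier dosimetry is not excluded, and nothing requires the re-check on which the smaller share depends.

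**There are other safeguards.** Two weeks is a minimum. Cycle 1 adverse events are entered within 24 hours (Appendix 2). The DMC receives all SAEs, and either it or the Sponsor Safety Committee can call an unplanned meeting (4.4). The sponsor can halt dosing (4.4.1), and significant safety issues go to the Medical Monitor and on to the DMC (7.4.5.6). These lower the risk. None is an automatic hold, and a Grade 4 count without symptoms is not necessarily an SAE under Section 7.4.2.

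**The sponsor chose to tolerate short Grade 4 cytopenias.** True, and that threshold can stay. The point concerns an event whose duration is still unknown when dosing is cleared.

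**A reader might infer the same gap at the close of the 5-week window.** The documents largely settle that. Section 3.1.1.2 is best read as attributing a DLT by onset, although 3.1.1.1 and 8.5.1 use looser wording. The DMC makes the final DLT call and reviews after Cycle 1, and Section 7.4.5.5 has related events of Grade 3 or higher followed until resolved, chronic or stable. The next level's earliest escalated dose is on Day 36 + 7 = Day 43 of the last patient's clock, when 0–1 of 28 onset days (0–4%) remain undecided if re-checked.

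**Conclusion.** The gap is real and narrow. As written, the rule can clear two further treatments at Dose Levels 2–5, without DMC feedback, while the first child has an ongoing Grade 4 anemia, neutropenia or non-bleeding thrombocytopenia that began on post-treatment days 7–14. The undecided share of onset days is 50–57% if the next patients have already had dosimetry by Day 22, and 0–7% if dosimetry waits and the event is re-checked. The loss is the stagger before the third child (12 days shorter) and a DMC look. A confirmed sentinel DLT would not have barred the second patient.

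Three stronger readings are tempting and not supported. The first is that about half of sentinel events or patients would be missed: the shares count calendar days, and the documents give no human onset timing. The second is that the dose-escalation decisions or the MTD are compromised: no such effect can be derived. The third is that any Grade 4 cytopenia slips through: bleeding thrombocytopenia and other Grade 4 hematological events do not face the 1-week test.

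The conclusion assumes nominal visit days and the visible text. The DMC Charter is not among the documents, Figure 1 is not shown, and a figure in the list of adverse events of special interest (7.4.4) is missing. A hold could be written in the Charter or in Figure 1, though Section 4.4 itself waives DMC feedback at this step.

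**What to change.** In Sections 3.1.1.1 and 4.4, add: if the first patient at a level has ongoing Grade 4 anemia, thrombocytopenia or neutropenia two weeks after treatment, no further patient receives the treatment dose at that level until the event has fallen below Grade 4 or the DMC has reviewed it. Add to Table 6 that blood counts are repeated after such a value until its duration is settled.

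The DLT thresholds stay as they are, and no patients are added. The cost is protocol wording, matching wording in the DMC Charter, a few extra blood counts in affected children, and an occasional delay. Under the 1-week limb the delay is usually about a week. Where the limb of more than 3 weeks following intervention applies, waiting for the duration to be settled could take longer, and DMC review caps the delay. A rule barring escalation to the next level until every pending event is decided is not needed.

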### **3.1.2. Maximum Tolerated Dose and Recommended Phase II Dose Definition**

The MTD is identified as the highest non-toxic dose level on which 6 patients have been treated, i.e., the dose level immediately below that at which 2 or more DLTs were observed and dose escalation was stopped. If only 3 patients were treated at the immediately lower dose level, 3 additional patients will be recruited at this dose level to ensure that no more than 1 DLT occurs out of 6 patients.

The RP2D will be defined as the highest tolerable dose, MTD, or a lower dose. For example, the RP2D may be lower than the MTD if accumulated toxicity over 2 cycles at the MTD is judged or proved to be non-tolerable.

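### An RP2D at the highest planned dose can rest on 0 DLTs in 3 patients, because the six-patient standard applies only to a level named as MTD

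*Combined protocol and SAP*

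**What the plan says.** Section 3.1.1.1 sets the escalation rules for the planned levels of 10, 25, 50, 65 and 85 mCi. Dose Level 1 starts with one patient; the others follow a 3+3 scheme.

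- No DLT in the first three patients: the next level opens, and "Dose escalation will continue in this manner until a DLT is observed or the highest planned dose level has been completed".
- One DLT in the first three: "If 1 DLT is observed in the initial 3-patients at each dose level, an additional 3 patients will" be enrolled there, if the DMC recommends it.
- A toxic level has been found: "If only 3 patients were treated at the dose level below the intolerable dose 3 more patients will be recruited at that dose level".
- Escalation ends either when a toxic level is identified or when "The highest planned dose level has been found to be tolerated", which the section explains as no stopping criterion having been met.

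Section 3.1.2 then defines the two outputs of Part 1. "The MTD is identified as the highest non-toxic dose level on which 6 patients have been treated", that is, the level just below the one that stopped escalation. If that level has only three patients, "3 additional patients will be recruited at this dose level to ensure that no more than 1 DLT occurs out of 6 patients". For the Part 2 dose, "The RP2D will be defined as the highest tolerable dose, MTD, or a lower dose". No number of patients is attached to this second definition. Section 3.2 adds that the choice rests mainly on safety and tolerability over both Part 1 cycles, again without a minimum number.

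**The concern.** Two routes lead to an RP2D. If a level proves toxic, the level below it must show at most one DLT in six patients before it is the MTD. If no level proves toxic, escalation simply runs out of levels. After 0/3 at 85 mCi there is no next level to open, no DLT to trigger expansion, and no toxic level above to trigger the top-up. The written rules end there, with three DLT-evaluable patients, and section 3.1.2 allows that level to be the RP2D.

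Section 3.1.3 then gives the RP2D to about 24 pediatric and adolescent patients for up to five cycles. At 85 mCi, five cycles total 5 × 85 = 425 mCi, against 5 + 2 × 85 = 175 mCi for a full Part 1 course including the dosimetry dose. DLTs are defined only for Cycle 1 of Part 1 (section 3.1.1.2), so Part 2 does not complete the count. Its one scheduled DMC meeting comes when the eighth patient has been dosed in Cycle 1 (section 4.4).

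**Working it through.** **The plan's own figure.** Section 8.1 estimates up to 25 patients in Part 1 over five dose levels. One patient at Dose Level 1 plus six at each of four levels gives 1 + 4 × 6 = 25, an exact match. With no DLT anywhere, the written rules give 1 + 4 × 3 = 13.

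**What the results at one level can exclude** (exact Clopper-Pearson, two-sided 95%). For zero events the upper limit is 1 − 0.025^(1/n).

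- 0/3: 1 − 0.025^(1/3) = 70.8%
- 0/6: 1 − 0.025^(1/6) = 45.9%
- 1/6: 64.1% (interval 0.4% to 64.1%)

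Both 0/6 and 1/6 pass the MTD standard, so both belong in the comparison.

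**Chance of accepting the top level once it is reached.** The true DLT rate p is an assumption; the documents state no target or expected rate. DLTs are taken as independent with a common rate, and expansion after 1/3 is taken to go ahead.

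- P(0/3) = (1 − p)³ and P(1/3) = 3p(1 − p)².
- Written rule: P(0/3) + P(1/3) × P(0/3).
- MTD standard, at most 1 in 6: P(0/3) × [P(0/3) + P(1/3)] + P(1/3) × P(0/3).
- Difference: P(0/3) × P(2 or 3 of 3).

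At p = 0.33, P(0/3) = 0.67³ = 0.301 and P(1/3) = 3 × 0.33 × 0.67² = 0.444. The written rule gives 0.301 + 0.134 = 0.434. The MTD standard gives 0.224 + 0.134 = 0.358.

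| True DLT rate | P(0/3) | P(1/3) | Written rule | MTD standard | Difference (points) |
|---|---|---|---|---|---|
| 10% | 0.729 | 0.243 | 0.906 | 0.886 | 2.0 |
| 20% | 0.512 | 0.384 | 0.709 | 0.655 | 5.3 |
| 30% | 0.343 | 0.441 | 0.494 | 0.420 | 7.4 |
| 33% | 0.301 | 0.444 | 0.434 | 0.358 | 7.7 |
| 40% | 0.216 | 0.432 | 0.309 | 0.233 | 7.6 |
| 50% | 0.125 | 0.375 | 0.172 | 0.109 | 6.3 |

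**How often 0/3 is the basis.** The share of acceptances resting on 0/3 is 1 / [1 + P(1/3)]. That is 1/1.243 = 80% at a true rate of 10% and 1/1.444 = 69% at 33%, so over this range 0/3 is the usual path to a top-level RP2D.

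**What three more patients would show.** After 0/3, the chance that a further three include two or more DLTs, and so fail the MTD standard, is 22% at a true rate of 30% and 35% at 40%.

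**The case against.** The strongest reply is that 0/3 permits a top-level RP2D but does not compel one. The RP2D draws on both Part 1 cycles (section 3.2) and may be set below the MTD (section 3.1.2). Under section 4.4 the DMC may recommend holding at the same level, and it reviews cumulated absorbed dose and all Part 1 toxicity before judging whether five cycles are feasible. Part 2 adds the eighth-patient review, the hold rules in section 4.4.1 and individual dose reductions (section 5.3.1). Section 3.2 also gives a reason for three-patient levels: to limit unnecessary exposure. All of this stands and limits the weight of the point. None of it sets a minimum number of patients, and the hold rules rest on judgment. I have not seen Figure 1 or the DMC Charter; either might state a rule for the top level.

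The numerical effect is also small. The worst result that passes moves only from an upper limit of 71% (0/3) to 64% (1/6), and a dose with a 33% DLT rate would still pass more than a third of the time.

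Two stronger readings are tempting and fail.

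- A reader might infer that every lower level needs six patients, so that the standard is weakest at the highest dose. It does not: any level from 2 upward can be passed on 0/3, Dose Level 1 can be passed on one patient, and an RP2D set below the MTD has no stated minimum either. Six patients are required only of a level named as MTD.
- A reader might infer that sections 3.1.1.1 and 3.1.2 contradict each other on the RP2D. Section 3.1.1.1 does not mention the RP2D, and on the MTD the two sections agree.

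**Conclusion.** The point holds as a gap between two routes to the Part 2 dose. The protocol sets an evidence standard for the MTD and none for an RP2D chosen without an MTD, so the rules followed as written can deliver a top-level RP2D on three DLT-evaluable patients. This goes beyond missing detail, because 0/3 is a likely path when no level proves toxic. The consequence is moderate: about 2 to 8 percentage points in the probability of accepting the top level, for assumed true DLT rates from 10% to 50%. It should be corrected before the RP2D is chosen, but it does not undermine the escalation design.

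**What to change.** Reconcile sections 3.1.1.1 and 3.1.2. State the number of DLT-evaluable patients and the DLT limit that must support an RP2D selected without an MTD, including one at the highest planned level. The candidate already in the protocol is its own MTD standard. If the sponsor and DMC intend a different one, the protocol should state it and justify it; that choice is theirs.

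Applying the MTD standard costs up to three more patients on the 0/3 path, plus the time to observe them. With no DLT at any level, Part 1 grows from 13 to 1 + 3 × 3 + 6 = 16. The estimated maximum of 25 is consistent with 1 + 4 × 6, so it has room for six at the top level. It could be exceeded if Dose Level 1 expands (3 + 24 = 27), if an intermediate level is added (1 + 5 × 6 = 31), or if patients are replaced.

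Counting the first Part 2 patients toward the six would not be an equivalent shortcut. They receive no dosimetry dose, enter under a different recurrence limit (one rather than two), and have no DLT definition.
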